1.0 TRIAL SUMMARY

Abbreviated Title	Pembrolizumab and Olaparib in Cervical Cancer Patients
Trial Phase	II
Clinical Indication	Cervical Cancer
Trial Type	Therapeutic
Type of control	None
Route of administration	Intravenous and Oral
Trial Blinding	None
Treatment Groups	One
Number of trial participants	48
Estimated enrollment period	2-3 years
Estimated duration of trial	3-4 years
Duration of Participation	Until lack of clinical benefit is demonstrated.
Estimated average length of treatment per patient	6 months

2.0 TRIAL DESIGN

The study is a non-randomized, open-label phase II clinical trial of the PD-1 inhibitor pembrolizumab, in combination with the PARP inhibitor olaparib, in patients with stage IV, unresectable or recurrent cervical cancer after failure of first-line therapy.

Patients will be treated with standard doses of pembrolizumab, 200 mg intravenously (IV) every 3 weeks [Chung et al., 2019], which is approved for metastatic cervical cancer patients with PDL-1 expression (CPS ≥ 1) and disease progression on or after chemotherapy. They will also receive olaparib 300mg orally (PO) twice daily (BID), which is the FDA approved dose for treatment of BRCA positive ovarian and breast cancers [Barber et al., 2013; Swisher, 2008; Bouwman et al., 2010; Robson et al., 2017]. One cycle is defined as 3 weeks or 21 days, and both drugs will be started on day 1 of cycle 1. Treatment will be continued until progressive disease or unacceptable toxicity. Evaluation for response with imaging (CT or MRI) will be performed every 9 weeks (3 cycles) using Immune Response Evaluation Criteria (iRECIST) [Seymour et al., 2017]. By this set of criteria, progression will need confirmation with a repeat scan at least four weeks later to rule out the rare but occasionally seen pseudo-progression. New lesions are added to the total burden of disease and only by themselves do not represent progression.

Treatment beyond initial investigator-assessed iRECIST-defined progression will be permitted in a case-by-case basis if the treating physician can document that the patient is experiencing clinical benefit and is tolerating study therapy.

Overlapping toxicities to the combination are not expected. However, the first six patients on the study will be evaluated for any grade 4 hematologic or grade 3 or higher non-hematologic toxicity during the first two cycles of treatment. Adjustment of the doses of olaparib to 300 mg PO daily will be made in subsequent patients if grade 4 hematologic toxicities lasting longer than 7 days, neutropenic fevers or grade 3 non-hematologic toxicities lasting longer than 7 days are observed in at least three of the initial

[figure not shown]
six patients. If intolerable toxicities arise after three or more cycles in patients otherwise experiencing clinical benefit, patients will have the option of continue pembrolizumab as monotherapy. Special attention will be placed on persistent grade 3 or higher anemia, as myelodysplastic syndromes have been described in around 1.5% of patients receiving olaparib in previous trials[Pujade-Lauraine et al., 2017; Robson et al., 2017; Ledermann et al., 2012; Moore et al., 2014]. Hematologic consultation (with bone marrow aspiration as needed) will be requested for patients developing persistent anemia.

Patients will be followed for three (3) years or until time of death. ORR, PFS, and OS will be determined. Correlative studies will determine the functional status of the Fanconi Anemia pathway promoting homologous recombination repair as well as the microbiome composition in responsive and non-responsive patients. In addition, tumor mutation burden, MSI, and PD-L1 expression will be correlated with Fanconi Anemia pathway status and response to therapy.

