Olaparib Dose Modification

Olaparib Dose Reductions

In case a dose reduction is necessary, olaparib will be administered as follows:

Table 3a Dose reductions for study treatment to manage adverse events

Initial Dose	Following re-challenge post interruption: Dose reduction 1	Dose reduction 2
300 mg twice daily	250 mg twice daily	200 mg twice daily

Table 3b Dose reduction for study treatment if patient develops moderate renal impairment

Initial Dose	Moderate renal impairment (calculated creatinine clearance by Cockcroft -Gault equation or based on a 24 hour urine test between 31 and 50 ml/min): Dose reduction
300 mg twice daily	200 mg twice daily

Table 3c Dose reductions for study treatment if patient has to start taking a strong or moderate CYP3A inhibitor

Initial Dose	Strong CYP3A inhibitor	Moderate CYP3A inhibitor
300 mg twice daily	100 mg twice daily	150 mg twice daily

For guidance on dose reductions for management of AEs (including renal impairment), refer to section 6.2.

For guidance on dose reductions when concomitant strong or moderate CYP3A inhibitors cannot be avoided see section 6.5.

When dose reduction is necessary patients will take one 150 mg tablet and one 100 mg tablet twice daily or two x 100 mg tablet twice daily (see Section 8.4.6), or one 150 mg tablet twice daily or one 100 mg tablet twice daily (see Section 6.5).

Pembrolizumab Dose Modification

AEs associated with pembrolizumab exposure may represent an immunologic etiology. These immune-related AEs (irAEs) may occur shortly after the first dose or several months after the last dose of pembrolizumab treatment and may affect more than one body system simultaneously. Therefore, early recognition and initiation of treatment is critical to reduce complications. Based on existing clinical study data, most irAEs were reversible and could be managed with interruptions of pembrolizumab, administration of corticosteroids and/or other supportive care. For suspected irAEs, ensure adequate evaluation to confirm etiology or exclude other causes. Additional procedures or tests such as bronchoscopy, endoscopy, skin biopsy may be included as part of the evaluation. Dose modification and toxicity management guidelines for irAEs associated with pembrolizumab are provided in Table 4.

Table 4 Dose modification and toxicity management guidelines for immune-related AEs associated with pembrolizumab

General instructions:				

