Table 6 Prohibited medications

Prohibited medication/class of drug:	
Anticancer therapy:	Not permitted while the patient is receiving study medication
Chemotherapy	
Immunotherapy	
Hormonal therapy*	
Radiotherapy (except palliative)	
Biological therapy	
Other novel agents	
Live virus vaccines	Not permitted while the patient is receiving study medication and during the 30 day follow up period.
Live bacterial vaccines	An increased risk of infection by the administration of live virus and bacterial vaccines has been observed with conventional chemotherapy drugs and the effects with olaparib are unknown.

*Hormone Replacement Therapy (HRT) is acceptable

Restricted concomitant medications

Table 7 Restricted concomitant medications

Medication/class of drug:	Usage (including limits for duration permitted and special situations in which it's allowed):

Table 7 Restricted concomitant medications

Medication/class of drug:	Usage (including limits for duration permitted and special situations in which it's allowed):
Strong CYP3A inhibitors: itraconazole, telithromycin, clarithromycin, boosted protease inhibitors, indinavir, saquinavir, nelfinavir, boceprevir, telaprevir	Strong or moderate CYP3A inhibitors should not be taken with olaparib. If there is no suitable alternative concomitant medication then the dose of olaparib should be reduced for the period of concomitant administration. The dose reduction of olaparib should be recorded in the CRF with the reason documented as concomitant CYP3A inhibitor use.
Moderate CYP3A inhibitors: ciprofloxacin, erythromycin, diltiazem, fluconazole, verapamil	
 • Strong CYP3A inhibitors – reduce the dose of olaparib to 100 mg twice daily for the duration of concomitant therapy with the strong inhibitor and for 5 half lives afterwards. • Moderate CYP3A inhibitors - reduce the dose of olaparib to 150 mg twice daily for the duration of concomitant therapy with the moderate inhibitor and for 3 half lives afterwards. • After the washout of the inhibitor is complete, the olaparib dose can be re-escalated.
Strong inducers: phenobarbital, phenytoin, rifampicin, rifabutin, rifapentine, carbamazepine, nevirapine, enzalutamide and St John's Wort	Strong or moderate CYP3A inducers should not be taken with olaparib. If the use of any strong or moderate CYP3A inducers are considered necessary for the patient's safety and welfare this could diminish the clinical efficacy of olaparib.

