6.2 Adverse Events (AEs), Serious Adverse Events (SAEs), and Other Reportable Safety Events

The definitions of an AE or SAE, as well as the method of recording, evaluating, and assessing causality of AE and SAE and the procedures for completing and transmitting AE, SAE, and other reportable safety event reports can be found in Appendix 5.

Adverse events, SAEs, and other reportable safety events will be reported by the participant (or, when appropriate, by a caregiver, surrogate, or the participant's legally authorized representative).

The investigator and any designees are responsible for detecting, documenting, and reporting events that meet the definition of an AE or SAE as well as other reportable safety events. Investigators remain responsible for following up AEs, SAEs, and other reportable safety events for outcome.

The investigator, who is a qualified physician, will assess events that meet the definition of an AE or SAE as well as other reportable safety events with respect to seriousness, intensity/toxicity and causality.

Olaparib

Any toxicity observed during the course of the study could be managed by interruption of the dose of study treatment or dose reductions. Repeat dose interruptions are allowed as required, for a maximum of 4 weeks on each occasion. If the interruption is any longer, the study team must be informed. Study treatment can be dose reduced to 250 mg twice daily as a first step and to 200 mg twice daily as a second step. If the reduced dose of 200 mg twice daily is not tolerable, no further dose reduction is allowed and study treatment should be discontinued.

Once dose is reduced, escalation is not permitted (except following concomitant treatment with CYP3A4 inhibitors – see Section 6.5

6.2.1 Time Period and Frequency for Collecting AE, SAE, and Other Reportable Safety Event Information

All AEs, SAEs, and other reportable safety events that occur after the consent form is signed but before intervention allocation/randomization must be reported by the investigator if the participant is receiving placebo run-in or other run-in treatment, if the event cause the participant to be excluded from the study, or is the result of a protocol-specified intervention, including but not limited to washout or discontinuation of usual therapy, diet, or a procedure.

- All AEs from the time of intervention allocation/randomization through 30 days following cessation of study intervention must be reported by the investigator.

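### If the run-in rule cuts later patients to olaparib 300 mg daily, the toxicity and renal reduction steps that name no starting dose all point to a dose above the one they are taking

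*Combined protocol and SAP*

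**What the plan says.** **Run-in rule.** Sections 2.0 and 4.2.2 assess the first six patients over two cycles. If three or more have grade 4 hematologic toxicity beyond 7 days, neutropenic fever, or grade 3 non-hematologic toxicity beyond 7 days, then "Adjustment of the doses of olaparib to 300 mg PO daily will be made in subsequent patients".

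**Toxicity steps.** Section 6.2 sets two steps down from the planned 300 mg twice daily: 250 mg twice daily, then 200 mg twice daily. It closes the ladder with "If the reduced dose of 200 mg twice daily is not tolerable, no further dose reduction is allowed and study treatment should be discontinued". It adds "Once dose is reduced, escalation is not permitted", with an exception after CYP3A4 inhibitor use. Table 12 (hemoglobin below 8 g/dl) and Table 13 (repeat grade 3-4 neutropenia, leukopenia or thrombocytopenia), both in Section 6.2.1.1, direct the same two steps. Section 6.2.1.2 offers them for non-hematologic toxicity.

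**Renal step.** Table 3b ("Dose reduction for study treatment if patient develops moderate renal impairment") and Section 6.2.1.3 give 200 mg twice daily. Section 6.2.1.3 then leaves the decision to the investigator.

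**Starting dose.** Tables 3a, 3b, 3c and 14 list 300 mg twice daily as the only initial dose. The text of Sections 6.2, 6.2.1.2 and 6.2.1.3, Tables 7, 12 and 13, and the tablet instruction after Table 3c ("When dose reduction is necessary patients will take one 150 mg tablet and one 100 mg tablet twice daily") carry no starting-dose condition.

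**The concern.** The run-in branch creates a second possible starting dose, and the dose-modification rules were written for the first one only. A patient started at 300 mg daily is already below the bottom of the ladder. If her hemoglobin falls below 8 g/dl and recovers, Table 12 tells the site to reduce to a dose higher than the one she was taking. The instruction cannot be carried out as a reduction, and no other text says what to do instead.

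This is more than a missing detail, because a directive table gives a wrong dose for these patients. They are the group whose dose was cut because the regimen had proved toxic. The trial is multi-center (Section 2.1), so sites could resolve the conflict differently: resume 300 mg daily, use an unlisted lower dose, or stop olaparib. Section 7.2 plans to summarize dose reductions and relative dose intensity, so uneven handling would carry into the safety report.

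**Working it through.** The plan gives no figure of its own for this point. The only design figure used is the enrolment of 48 (Section 7.2).

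**1. Daily totals** (mg per dose × doses per day), compared with the 300 mg/day run-in dose. Section 2.0 does not say whether 300 mg daily is one dose or two of 150 mg; the total is the same.

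| Dose named | Where | mg/day | Against 300 mg/day |
|---|---|---|---|
| 300 mg twice daily | planned start | 600 | – |
| 250 mg twice daily | 6.2, 6.2.1.2, Tables 12 and 13 | 500 | 500/300 = 1.67, +67% |
| 200 mg twice daily | same, and renal step in 6.2.1.3 | 400 | 400/300 = 1.33, +33% |
| 150 mg twice daily | Table 7, moderate CYP3A inhibitor | 300 | no change |
| 100 mg twice daily | Table 7, strong CYP3A inhibitor | 200 | 200/300 = 0.67, −33% |

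Gap to the toxicity floor: 400 − 300 = 100 mg/day, and 100/400 = 25%. Every toxicity and renal step is above the run-in dose. The only dose below it is the strong-inhibitor adjustment, which is for drug interaction and not for toxicity.

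**2. Which steps are directive?**
- Table 12, hemoglobin below 8 g/dl: directive after recovery.
- Table 13, repeat grade 3-4 event: directive.
- Table 12, later grade 2 anemia: reduction may be considered.
- Section 6.2.1.2: reduction is considered when toxicity recurs after re-challenge and further interruption is inadequate; permanent discontinuation is the alternative.
- Section 6.2.1.3: reduction recommended, then left to investigator discretion.
- Table 12, first grade 2 anemia, and Table 13, first grade 3-4 event: no reduction is called for, so a same-dose restart fits.

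The firm conflict is therefore in the first two items.

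**3. Does the escalation ban settle it?** The sentence applies once a dose has been reduced. A patient who begins at 300 mg daily has had no reduction of her own, so its application to her is unclear.

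**4. How many patients?** 48 − 6 = 42 could at most start at 300 mg daily. No enrolment pause after patient six is stated, so some may start at full dose while the first six are assessed.

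**5. How likely is the rule to fire?** The documents give no rate for the trigger toxicities, so the per-patient rate p is an assumption. With six patients, P(X ≥ 3) = 1 − Σ C(6,k) p^k (1−p)^(6−k), summed over k = 0, 1, 2. For p = 0.20: 1 − (0.2621 + 0.3932 + 0.2458) = 0.099.

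| Assumed p | P(rule fires) |
|---|---|
| 0.10 | 0.016 |
| 0.20 | 0.099 |
| 0.30 | 0.256 |
| 0.40 | 0.456 |
| 0.50 | 0.656 |

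**The case against.** The best defense is that the protocol already implies the answer. Section 6.2 stops olaparib when 200 mg twice daily is not tolerated; a patient below 400 mg/day is past that floor, so discontinuation follows. This is the natural reading, and the fix builds on it. It remains an inference: the sentence speaks of a patient reduced to that dose, and Tables 12 and 13 say something different without qualification.

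It is also fair that the problem depends on two events, that overlapping toxicity is not expected (Section 2.0), and that other safeguards still apply: the interruption limits, the stop rule when counts do not recover within 4 weeks, and pembrolizumab alone after three or more cycles with benefit. Those points limit the reach. They do not supply the olaparib step after a recovered hemoglobin below 8 g/dl.

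Three stronger readings are tempting, and the documents do not support them:
- *A reader might infer that 42 patients are left without a rule.* Forty-two is a ceiling on who could start at 300 mg daily. Only those who then need a reduction meet the gap.
- *A reader might infer that no recovery in this cohort has a usable rule.* First grade 3-4 cytopenia and first grade 2 anemia can be handled by interruption and same-dose restart.
- *A reader might infer that the protocol would raise doses, or that the escalation ban flatly contradicts the tables.* The steps are worded as reductions, so an actual increase is unlikely. The ban is too unclear for this cohort to count as a firm conflict or a firm safeguard.

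The CYP3A doses are a minor matter. These inhibitors are excluded at entry and are to be avoided on treatment, and the strong-inhibitor dose is still a true reduction.

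**Conclusion.** The point holds in a limited form. If the run-in rule fires, later patients start 100 mg/day (25%) below the toxicity floor. Two directive steps (Table 12 for hemoglobin below 8 g/dl, Table 13 for repeat grade 3-4 cytopenia) and the discretionary toxicity and renal steps then name doses 33% or 67% above the current one. Those percentages measure the conflict in the text; they are not a forecast of dose increases. The reach is conditional: the rule must fire, with a probability from about 0.02 to 0.66 over assumed toxicity rates of 10% to 50%, and a patient must then need a reduction. The number who would do so cannot be estimated from the documents. The sample size, decision rule and response analysis are unaffected. The change is worth making because it is cheap and concerns the safe dosing of a group already cut for toxicity.

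**What to change.** Amend the wording before the run-in decision after the first six patients:

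1. Limit the 250 and 200 mg twice daily toxicity steps (Sections 6.2 and 6.2.1.2, Tables 12 and 13, and the tablet instruction after Table 3c) and the 200 mg twice daily renal step (Section 6.2.1.3) to patients who started at 300 mg twice daily. Tables 3a, 3b and 14 already list only that starting dose.
2. For patients who started at 300 mg daily, keep the existing interruption and same-dose restart rules.
3. Where the rules call for a dose reduction in these patients, discontinue olaparib, in line with the Section 6.2 floor rule, or use one lower dose named by the sponsor. The 100 and 150 mg tablets in Table 15 make a lower dose feasible, but the documents hold no data to choose one.
4. State that these patients are never moved to a higher daily dose.
5. Leave any CYP3A inhibitor dose for this cohort to the sponsor; the documents do not support scaling the current doses by ratio.

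The cost is protocol text only, with no change to the run-in dose, sample size or analysis. The downside is that some patients may stop olaparib earlier than if sites improvised.

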2.1 Trial Design

The study is a non-randomized, open-label, multi-center, phase II clinical trial of the PD-1 inhibitor pembrolizumab, in combination with the PARP inhibitor olaparib, in patients with stage IV, unresectable or recurrent cervical cancer after failure of first-line therapy.

2.2 Trial Schema

2.3 Schedule of Activities

Trial Period:	Screening Phase	Treatment Cycles ^a								End of Treatment	Post-Treatment		
		1	2	3	4	To be repeated beyond 8 cycles					Discon	Safety Follow-up	Follow Up Visits ^b
Treatment Cycle/Title:	Screening					5	6	7	8				
Scheduling Window (Days):	-28 to -1		± 3	± 3	± 3	± 3	± 3	± 3	± 3	At time of Discon ±7	30 days post discon ±7	Every 8 weeks post discon ± 7	Every 12 weeks ±7
Administrative Procedures													
Informed Consent	X												
Inclusion/Exclusion Criteria	X												
Demographics	X												
Medical History	X	X	X	X	X	X	X	X	X				

Trial Period:	Screening Phase	Treatment Cycles ^a								End of Treatment	Post-Treatment			
		1	2	3	4	To be repeated beyond 8 cycles					Safety Follow-up	Follow Up Visits ^b	Survival Follow-Up	
Treatment Cycle/Title:	Screening	1	2	3	4	5	6	7	8	Discon	At time of Discon ±7	30 days post discon ±7	Every 8 weeks post discon ± 7	Every 12 weeks ±7
Scheduling Window (Days):	-28 to -1		± 3	± 3	± 3	± 3	± 3	± 3	± 3					
Prior and Concomitant Medication Review	X	X	X	X	X	X	X	X	X					
Trial Treatment Administration		X	X	X	X	X	X	X	X					
Post-study anticancer therapy status												X	X	
Survival Status												X	X	X
Clinical Procedures/Assessments														
Review Adverse Events			X	X	X	X	X	X	X					
Full Physical Examination	X													
Directed Physical Examination			X	X	X	X	X	X	X					
Vital Signs and Weight	X	X	X	X	X	X	X	X	X					
ECOG Performance Status	X	X	X	X	X	X	X	X	X					
Laboratory Procedures/Assessments: analysis performed by LOCAL laboratory														
Pregnancy Test – Urine or Serum β-HCG	X ^c													
PT/INR and aPTT	X ^a													
CBC with Differential	X ^a	X ^b	X	X	X	X	X	X	X					
Comprehensive Serum Chemistry Panel	X ^a	X ^b	X	X	X	X	X	X	X					
Urinalysis	X ^a													
T3, FT4 and TSH	X ^a				X			X ^f						
Efficacy Measurements														
Tumor Imaging	X				X					X ^d	X			
Tumor Biopsies/Archival Tissue Collection/Correlative Studies Blood														
Archival or Newly Obtained Tissue Collection	X ^e													
Correlative Studies Stool Collection	X ^e				X ^e					X ^e				

^a Must be performed within 10 days of the first treatment visit (Cycle 1 Day 1).

^b Hematology (CBC with differential) and Creatinine results must be available and reviewed by the Investigator prior to infusion. A spot creatinine result may be used to proceed with treatment, as Chemistry results may not be available.

^c Must be performed within 72 hours of the first treatment visit (Cycle 1 Day 1).

^d Tumor imaging to be done every 9 weeks (within 1 week before every 4th cycle) and will only be required every 12 weeks for patients that have been on treatment for more than 1 year.

^e See Protocol Laboratory Manual.

^f Beginning with Cycle 9, T3, FT4 and TSH will be performed every 3 cycles/9 weeks.

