6.1.2.6 Tumor Imaging and Assessment of Disease

Tumor assessments will be performed by computer tomography (CT), PET/CT or Magnetic Resonance Imaging (MRI).

Tumor imaging is strongly preferred to be acquired by computed tomography (CT). For the abdomen and pelvis, contrast-enhanced magnetic resonance imaging (MRI) may be used when CT with iodinated contrast is contraindicated, or when local practice mandates it. MRI is the strongly preferred modality for imaging the brain. The same imaging technique regarding modality, ideally the same scanner, and the use of contrast should be used in a participant throughout the study to optimize the reproducibility of the assessment of existing and new tumor burden and improve the accuracy of the assessment of response or progression based on imaging.

Scans obtained prior to consenting will be allowed, as long as performed within 21 days of study initiation. CT Scans or MRI's will be repeated every 3 cycles (3 weeks cycles); that is before every fourth dose of pembrolizumab in order to assess response to therapy. Tumor imaging will only be required every 12 weeks for patients that have been on treatment for more than 1 year. Immune Response Evaluation Criteria (iRECIST) [36] will be utilized for assessment of response to therapy.

Expedited confirmation of measurable disease based on RECIST 1.1 at Screening should be used to determine participant eligibility. Confirmation that the participant's imaging shows at least 1 lesion that is appropriate for selection as a target lesion per RECIST 1.1 is highly recommended prior to participation allocation.

Participant eligibility will be determined using local assessment (Investigator assessment) based on RECIST 1.1. In addition, images (including via other modalities) that are obtained at an unscheduled time point to determine disease progression, as well as imaging obtained for other reasons, but which demonstrate radiologic progression, should also be used to determine progression.

When the Investigator identifies radiographic progression per RECIST 1.1, efforts should be made to verify radiologic PD. Treatment should continue until PD has been verified. Regardless of whether PD is verified, if the Investigator considers the participant has progressed, but elects to implement iRECIST, the Investigator will assess for confirmation of progression by iRECIST at subsequent time points.

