6.1.2.6.2 Tumor Imaging During the Study

The first on-study imaging assessment should be performed at 9 weeks (± 7 days) from the date of first dose. Subsequent tumor imaging should be performed every 9 weeks (± 7 days) or more frequently if clinically indicated. After 52 weeks (± 7 days), participants who remain on treatment will have imaging performed every 12 weeks (± 7 days). Imaging timing should follow calendar days and should not be

adjusted for delays in cycle starts. Imaging should continue to be performed until disease progression is identified by the Investigator.

Objective response should be confirmed by a repeat imaging assessment. Tumor imaging to confirm PR or CR should be performed at least 4 weeks after the first indication of a response is observed. Participants will then return to regular scheduled imaging every 9 weeks, starting with the next scheduled imaging time point. Participants who receive additional imaging for confirmation do not need to undergo the next scheduled tumor imaging if it is less than 4 weeks later; tumor imaging may resume at the subsequent scheduled imaging time point.

Per iRECIST (Section 7.1.2.6.6), disease progression should be confirmed by the site 4 to 8 weeks after first radiologic evidence of PD in clinically stable participants. Participants who have unconfirmed disease progression may continue on treatment at the discretion of the investigator until progression is confirmed by the site provided they have met the conditions detailed in Section 7.1.2.6.6. Participants who receive confirmatory imaging do not need to undergo the next scheduled tumor imaging if it is less than 4 weeks later; tumor imaging may resume at the 1.2.6.6.subsequent scheduled imaging time point, if clinically stable. Participants who have confirmed disease progression by iRECIST, as assessed by the site, will discontinue study treatment. Exceptions are detailed in Section 7.

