Kaplan-Meier curves will be used to estimate the distributions of overall survival and immune-related progression-free survival (iPFS). Point estimates and 2-sided 95% confidence intervals will be reported for selected times using Greenwood's variance and the log-log transform method. This will include the 20-week iPFS for purposes of comparison. Based on the panel sequencing results, somatic alterations will be summarized and reported as proportions for genes in FA competent and FA functionally deficient tumors. Confidence intervals will be calculated using the exact method. Additional analyses will be done to establish relationships between treatment and certain baseline characteristics, including deficiencies in the FA pathway, PD-L1 expression, TMB, other deficiencies in DNA damage repair mechanisms. These relationships will be explored primarily through logistic regression or cox proportional hazards regression, depending on the outcome of interest.

For known or predicted deleterious mutations of suspected inheritance trait detected during the trial, the process would be aided by making sure that patients carrying these mutations get referred for genetic counseling and CLIA certified germline analysis. The Miami Cancer Institute has these services readily available.

Stool Microbiome Data Analyses: Centered log-ratio (CLR) transformations will be applied to microbiome data. Log-ratios make the data symmetric and linearly related, and places the data in a log-ratio coordinate space. Thus, we can obtain information about the log-ratio abundances of features relative to other features in the compositional dataset. Zero counts of operational taxonomic units (OTU) will be converted to a probability vector prior to centered log-ratio transformation. Aitchison distance, which is simply the Euclidian distance between samples after CLR transformation, and the distances between samples same as the phylogenetic isometric log-ratio (ILR), will be calculated and used for clustering and ordination. Compositional principal component analysis (PCA) will be applied and biplots will be used to display the relationships between OTUs and the distances between samples.

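### On-treatment scans are tied to cycles in some sections and to calendar weeks in another; where a site follows the cycle wording, a pembrolizumab delay can push the week-18 scan past the 20-week iPFS landmark

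*Combined protocol and SAP*

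**What the plan says.** Four places set the timing of scans during treatment.

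- Section 2.0: "Evaluation for response with imaging (CT or MRI) will be performed every 9 weeks (3 cycles", so weeks with a gloss in cycles.
- Section 2.3, Schedule of Activities, footnote d: "Tumor imaging to be done every 9 weeks (within 1 week before every 4th cycle", again weeks first, then a working window set by the cycle.
- Section 6.1.2.6: "CT Scans or MRI's will be repeated every 3 cycles (3 weeks cycles); that is before every fourth dose of pembrolizumab", so cycles and doses only.
- Section 6.1.2.6.2: "The first on-study imaging assessment should be performed at 9 weeks (± 7 days) from the date of first dose", then "Subsequent tumor imaging should be performed every 9 weeks (± 7 days) or more frequently if clinically indicated". It adds "Imaging timing should follow calendar days", and the same sentence excludes any shift for late cycle starts. After 52 weeks the interval becomes 12 weeks.

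Section 6.1 treats compliance with the Trial Flow Chart as mandatory. It places that chart in Section 6.0, but the only such table is in Section 2.3. No section gives an order of precedence.

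On the analysis side, SAP Section 7.2 plans Kaplan-Meier estimates of iPFS at selected times: "This will include the 20-week iPFS for purposes of comparison". It has no rule for late or off-schedule scans.

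**The concern.** Progression seen on imaging can only be dated to a scan, so the scan calendar is part of how PFS and iPFS are measured. If a scan moves whenever a pembrolizumab dose moves, the date on which progression can be recorded depends on dosing history. Section 2.1 describes a multi-center trial, so sites working from different sections could produce progression dates that are not comparable.

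The 20-week landmark is the sensitive place, because it falls just after the nominal week-18 scan. If that scan slips beyond week 20, a patient whose progression would have been seen at week 18 is counted as progression-free at 20 weeks. There is no control arm (Section 1.0), so any comparison of 20-week iPFS is with outside data, and an artifact of scan timing would not cancel.

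**Working it through.** **Plan's own figures.** The documents give no figure for 20-week iPFS, hold frequency or scan delay. The only design calculation is the iORR rule (48 patients, 10 or more responses). By exact binomial, P(X ≥ 10 | 0.13) = 0.0865 and P(X ≤ 9 | 0.28) = 0.0995, against 0.087 and 0.099 stated. Scan dates do not enter it.

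**Inputs from the documents.** A cycle is 3 weeks (Section 2.0). The calendar rule is every 9 weeks ± 7 days (Section 6.1.2.6.2). Interruptions of pembrolizumab for reasons other than treatment-related AEs should end within 3 weeks unless discussed with the sponsor (Section 5.2.2). An immune-related hold has an outer limit of 12 weeks from the last dose (Table 4). The next dose was due 3 weeks after that last dose, so the longest single slip is 12 − 3 = 9 weeks.

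**Step 1, no delay.** Cycle c starts at week 3(c − 1): cycle 4 at week 9, cycle 7 at week 18, cycle 10 at week 27. The texts agree.

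**Step 2, second scan after a slip of h weeks.** Under the calendar rule it stays at week 18 (window 17 to 19), before week 20. Under the cycle wording it is due at week 18 + h, and 18 + h > 20 when h > 2. Footnote d allows the week before the cycle, so for h = 3 the scan falls in weeks 20 to 21.

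**Step 3, first scan after an early slip.** If the slip comes before cycle 4, the first scan is at week 9 + h: week 12, 15 or 18 for h = 3, 6 or 9. In the 9-week case progression present by week 18 is still recorded before week 20, so the 20-week estimate does not change.

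**Step 4, size.** Assumptions, none from the documents: exponential time to progression with median m, S(t) = 2^(−t/m); a fraction f of patients with one slip; start of the slip uniform over weeks 0 to 18, so half fall before the first scan; no deaths; no unscheduled scans; every site follows the cycle wording. Recorded 20-week iPFS is S at the last scan before week 20. That scan is at week 18 under the calendar rule, at 9 + h after an early slip, and at 9 after a slip between the two scans. The overstatement is

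Δ = f × ½ × {[S(9 + h) − S(18)] + [S(9) − S(18)]}.

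Mid case, m = 13 and f = 0.20: S(9) = 0.619, S(12) = 0.527, S(15) = 0.449, S(18) = 0.383.

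| Slip | Calculation | Δ |
|---|---|---|
| 3 weeks | 0.20 × ½ × (0.144 + 0.236) | 3.8 points |
| 6 weeks | 0.20 × ½ × (0.066 + 0.236) | 3.0 points |
| 9 weeks | 0.20 × ½ × (0 + 0.236) | 2.4 points |

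Range over m = 10 to 26 and f = 0.10 to 0.30:

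- Lowest (m = 26, f = 0.10, 9 weeks): 0.10 × ½ × (0.787 − 0.619) = 0.8 points.
- Highest (m = 10, f = 0.30, 3 weeks): 0.30 × ½ × [(0.435 − 0.287) + (0.536 − 0.287)] = 6.0 points.

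In patients, 48 × 0.008 = 0.4 and 48 × 0.060 = 2.9.

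**Step 5, median PFS.** Simulation under the same assumptions covered 3- and 6-week slips, four medians (10, 13, 20, 26 weeks) and three hold rates (10%, 20%, 30%), or 24 combinations. Recorded median PFS was unchanged in 22. It rose from 27 to 30 weeks in 2, both with a 26-week median and a 3-week slip.

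**The case against.** The strongest reply is that Section 6.1.2.6.2 is the most specific text and settles the matter, and that two of the three cycle passages also state 9 weeks. That stands to this extent: a site following it shifts no scan and creates no bias. It does not remove the conflict, because Section 6.1.2.6 is stated purely in cycles and doses, the flow chart is declared binding, and nothing ranks the sections.

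Other limits also stand. The 20-week iPFS is a descriptive estimate with no test or threshold. Deaths count as events, unscheduled images showing progression count, and earlier imaging is allowed when clinically indicated; each shrinks the effect. A hold of olaparib alone does not move a scan anchored to pembrolizumab doses.

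A reader might infer more than the documents support:

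- *That patients are scanned late and PFS is biased upward.* This is conditional on which passage a site follows, and median PFS barely moves.
- *That scans fall before cycles 4, 8 and 12 (weeks 9, 21, 33), leaving none between weeks 10 and 20 even without a delay.* The fourth-cycle and fourth-dose wording is loose enough to be misread this way, but the same sentences say 9 weeks or 3 cycles, which means cycles 4, 7 and 10.
- *That the longest hold does the most harm.* Step 3 shows that a 9-week slip before the first scan does not change the 20-week estimate.
- *That duration of response is lengthened.* Section 3.2 starts it at documented response, and a late scan can delay that start as well as the progression date, so the direction is not established.
- *That delay tracks toxicity.* The documents do not give the reasons for holds or their frequency.

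**Conclusion.** The inconsistency is real and in the current text. Its consequence is conditional: where a site follows the cycle wording, a pembrolizumab delay of more than about 2 weeks can move the nominal week-18 scan past week 20, and 20-week iPFS can then be overstated.

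The size is an assumption-based range of roughly 1 to 6 percentage points, equivalent to fewer than 3 of 48 patients. It supposes that all sites use cycle timing and ignores deaths and unscheduled scans, so the realized effect should be smaller. Confidence is high in the wording conflict and limited in the size. The point is worth correcting because the remedy is cheap; it does not threaten the primary analysis.

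**What to change.** Bring Section 2.0, footnote d of Section 2.3 and Section 6.1.2.6 into line with the protocol's own calendar rule in Section 6.1.2.6.2. Delete the cycle gloss in Section 2.0, the fourth-cycle window in footnote d, and the cycle and dose wording in Section 6.1.2.6. Show on-treatment scans in the Schedule of Activities as weeks from first dose: every 9 weeks ± 7 days (9, 18, 27, 36, 45), then every 12 weeks after week 52, not shifted for dose delays. State the first date after week 45 explicitly, since the present text could be read as 45 + 9 = 54, 45 + 12 = 57 or 52 + 12 = 64.

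A sentence in SAP Section 7.2 on late or missed scans would be a useful addition, but the reconciliation does not depend on it.

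The cost is protocol wording and one footnote, with no scans beyond those Section 6.1.2.6.2 already requires. The small downside is that a delayed patient's scan may not coincide with an infusion visit.
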